**LIST OF ABBREVIATIONS**

5-HT 3	5-hydroxytryptamine type 3
AC	Anthracycline-Cyclophosphamide
AE	Adverse Event
CINV	Chemotherapy-Induced Nausea and Vomiting
CNS	Central Nervous System
CP	Complete Protection
CR	Complete Response
CRO	Contract Research Organization
CRF	Case Report Forms
CTCAE	Common Terminology Criteria for Adverse Events
DMP	Data Management Plan
EC	Ethics Committee
ECOG	Eastern Cooperative Oncology Group
eCRF	Electronic Case Report Form
ED	Emergency Department
EDC	Electronic Data Capture
EMA	European Medicine Agency
EU	European Union
FDA	Food and Drug Administration
FDC	Fixed-Dose Combination
FLIE	Functional Living Index-Emesis
GCP	Good Clinical Practice
HEC	Highly Emetogenic Chemotherapy
HEOR	Health Economics Outcomes Research

ICH	International Conference on Harmonization
ICF	Informed Consent Form
MAH	Marketing Authorization Holder
MEC	Moderately Emetogenic Chemotherapy
NCCN	National Comprehensive Cancer Network
N/A	Not Applicable
N/D	Not Done
NK-1	Neurokinin-1
PALO	Palonosetron
RCT	Randomized Controlled Trial
PIPEDA	Personal Information Protection and Electronic Documents Act
SOP	Standard Operating Procedure
TEAE	Treatment-Emergent Adverse Events
VAS	Visual Analog Scale
RWE	Real World Evidence
NEPA	netupitant/palonosetron

---

**STUDY SYNOPSIS**

TITLE	A Phase IV, Real World Observational Study On The Use Of Akynzeo® (netupitant/palonosetron) For The Prevention Of Nausea and Vomiting in Oncology Patients Receiving Highly Emetogenic Chemotherapy (HEC) Over Multiple Cycles.
SHORT TITLE	Observational study on the use of Akynzeo® in patients receiving HEC
PROTOCOL NUMBER	CAN-PRO-NEPA-001
PHASE	IV
OBJECTIVES OF THE STUDY	To generate Real World Evidence (RWE) on the quality of life by means of the FLIE questionnaire on administration of Akynzeo™ in highly emetogenic chemotherapy (HEC), and to generate Real World Evidence in support of existing clinical trial data. The study will also assess effectiveness and safety of Akynzeo® in the real world setting for the prevention of Chemotherapy Induced Nausea and Vomiting (CINV) in patients receiving highly emetogenic chemotherapy).
INDICATION	Patients with chemotherapy-induced nausea and vomiting who are receiving chemotherapy with high emetogenic potential for a maximum of 2 days on account of various types of cancer.
NUMBER OF PATIENTS	Approximately 200 patients
STUDY DESIGN	Real World, Observational study
STUDY CENTRES	Multi-centre, up to 20 sites
PRIMARY OUTCOME:	
 
• Functional Living Index of Emesis (FLIE) – Quality of Life
 

SECONDARY OUTCOMES	
 
• Complete Response (CR: no emetic episodes and no use of rescue medication) - overall – 0-120 hours (Day 1 to Day 5)
 
• Severity of nausea (VAS) - daily
 
• Time to failure (time to first emetic episode or time to rescue)
 
• Use of rescue medication - daily
 
• Safety parameters (failure of CR, i.e., nausea and vomiting will not be included in the safety records)
 

EXPLORATORY OUTCOMES	
 
• HEOR (Health Economic and Outcomes research) parameters: 
 
• ER visits
 
• Hospitalizations
 
 
 
• WPAI-NV (Work Productivity Activity Impairment Scale – Nausea and Vomiting)
 

METHODOLOGY	
 
• FLIE Questionnaire to be completed by the patient at the end of the observation period (Day 5/120 hours post each cycle) for at least the first 4 consecutive cycles of chemotherapy (cycles 1-4)
 
• Patient Diary to be completed daily starting on the first day of chemotherapy treatment (Day 1) until 5 days post treatment (Day 5/120 hours post each cycle). Diary data for cycles 1 - 4 will be included in the study database
 
• WPAI-NV to be completed by the patient at the end of the observation period (Day 5/120 hours post each cycle) for at least the first four consecutive cycles of chemotherapy (cycles 1-4)
 
• eCRF will be used for data capture
 

TREATMENT	
Akynzeo® (300mg Netupitant/0.5mg palonosetron hydrochloride).
 
In accordance with the approved Canadian Product Monograph; 1 capsule of Akynzeo® administered orally approximately 1 hour prior to the start of each chemotherapy cycle.

INCLUSION CRITERIA	
 
• Patient scheduled to receive a highly emetogenic chemotherapy (HEC).
 
• Patient scheduled to receive antiemetic prevention with Akynzeo® according to the approved Canadian Product Monograph as deemed medically necessary by the participating physician independently from this study.
 
• Age ≥ 18 years.
 
• Women of childbearing potential must use effective contraception during therapy and up to one month after treatment with Akynzeo®.
 
• Patient (and/or patient's authorized legal representative) should understand the nature of the study and provide written informed consent prior to or at the screening visit.
 
• Patient is able and willing to comply with the study protocol for the entire length of the study and will follow all study requirements, procedures and complete all visits as required.
 
• Patient is participating in another clinical trial where antiemetic treatment is not pre-specified by the study protocol.
 

EXCLUSION CRITERIA (as per Contraindications in the approved Canadian Product Monograph)	
 
• Women of child bearing potential who are pregnant, planning on becoming pregnant or breast feeding.
 
• Hypersensitivity to active substances, excipients or other ingredients of Akynzeo®.
 
• Concomitant use of pimozone, terfenadine, astemizole, or cisapride.
 
• Patient is enrolled in another clinical trial where antiemetic treatment is pre-specified by the study protocol.
 

---

STUDY DURATION	This study will last approximately 20 months from 1 st patient enrolled until last patient has completed. The observation period for each subject will last 4-6 months.
RECRUITMENT PERIOD	Approximately 12 months
ANALYSIS	Descriptive statistics will be generated for the primary, secondary and exploratory endpoints.

Table 1: Time and event schedule

Activity	Screening/ Visit 1	Visit 2 Cycle 1	Visit 3 Cycle 2	Visit 4 Cycle 3	Visit 5 Cycle 4	Visit 6/Final visit
Time period	-28 days to Day 1, Cycle 1	Day 1 of Cycle 1	Day 1 of Cycle 2	Day 1 of Cycle 3	Day 1 of Cycle 4	Within 28 days of Cycle 4 or prior to start of next chemotherapy cycle
Informed consent	X					
Inclusion/Exclusion	X					
Demographics & Medical History	X					
Nausea assessment - physician	X					
Current treatments/medications	X					
Patient Kit (distribute and provide education on use)	X*					
Patient Assessments:						
Patient diary, including: 
 
• Nausea Severity Assessment
 
• Rescue medications
 
• Adverse Events
 
		X 	X 	X 	X 	
• Functional Living Index – Emesis (FLIE)		X 	X 	X 	X 	
• Work Productivity Activity Impairment Scale – Nausea and Vomiting (WPAI-NV)		X 	X 	X 	X 	
Patient Kit - collect and review diary and questionnaires			X	X	X	X
Concomitant medication		X	X	X	X	X
Adverse event		X	X	X	X	X
Study completion assessment/early discontinuation						X

\*Patient Kit can be distributed at Screening/Visit 1 or Visit 2. All assessments/training should be completed prior to chemotherapy treatment

 Patient completes diary on days 1-5 (0-120 hours) post chemotherapy cycle

 Patient completes FLIE and WPAI after day 5 of cycle

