## 2.2 Secondary Outcomes

The response to Akynzeo® and the necessity for use of a rescue medication will be recorded to evaluate effectiveness. The medicinal products used as rescue medication will also be recorded. The following parameters will be calculated from information recorded in the patient diary:

- Complete Response (CR): no emetic episode and no use of rescue medication in the overall period (0-120h/Day 1-5)
- Severity of nausea (daily from Day 1 to Day 5) using a VAS scale (Visual Analogue Scale)
- Time to failure (time to first emetic episode or time to rescue)
- Use of rescue medication (daily from Day 1 to Day 5)

The collection of safety data and adverse events AEs in connection with administration of Akynzeo® will be performed.

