## 3 STUDY DESIGN

### 3.1 Study Overview

This two year (approximately), multi-centre, prospective, observational real-world study is designed to collect data on the use of Akynzeo® (netupitant/palonosetron) for the prevention of nausea and vomiting in oncology patients receiving highly emetogenic chemotherapy (HEC).

The visit schedule is comprised of 6 study visits (Table 1):

- Visit 1/Screening (4 weeks to 0 weeks prior to Visit 2)
- Visit 2: (Day of/but prior to 1st chemotherapy treatment administration)

- Visit 3: (Day of/but prior to 2nd chemotherapy treatment administration)
- Visit 4: (Day of/but prior to 3rd, chemotherapy treatment administration)
- Visit 5: (Day of/but prior to 4th, chemotherapy treatment administration)
- Visit 6/Final Visit

Visit 1 and 2 can be combined as determined by the investigator. Patients will report the daily occurrence and intensity of nausea and vomiting, rescue medications, adverse events (excluding nausea and vomiting) in a diary from Day 1 (chemotherapy treatment day) to Day 5/time point 0-120 hours post chemotherapy administration of each observation period.

Safety events occurring between chemotherapy cycles will be reported by the patient. Patient will have a follow up period of 28 days post the last-chemotherapy cycle.

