### 6.7 Effectiveness Assessments

The response to Akynzeo® and the necessity for use of a rescue medication will be recorded to evaluate effectiveness. Any medicinal products used as rescue medication will also be recorded in the patient diary.

The following parameters will be recorded in the patient diary:

- Severity of nausea (daily from Day 1 to Day 5) using a VAS (Visual Analogue Scale)

- Time to failure (time to first emetic episode or time to rescue)
- Use of rescue medication (daily from Day 1 to Day 5)

Note: A Complete Response (CR) is defined as no emetic episode and no use of rescue medication during the observational period (Day 1 to Day 5).

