## 8 SAFETY ASSESSMENTS

Timely, accurate, and complete reporting and analysis of safety information from clinical studies are crucial for the protection of subjects, investigators, and the sponsor, and are mandated by regulatory agencies worldwide. Adverse events will be collected from the time a subject has signed an ICF and followed until the end of study-visit 6 (28 days post visit 5/last dose of Akynzeo®).

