### 8.1 Adverse Event Definitions

According to the currently valid Directive of the European Parliament and of the Council relating to the implementation of good clinical practice in the conduct of clinical studies on medicinal products for human use (2001/20/EC), an adverse event (AE) is “Any untoward medical occurrence in a patient or clinical study subject administered a medicinal product and which does not necessarily have a causal relationship with this treatment”. An AE could therefore be any unfavourable or unintended sign (for example, an abnormal laboratory finding), symptom or any disorder with a temporal relationship to the use of a medicinal product, regardless of whether or not it is considered to be related to use of the medicinal product.

In the context of this study, all adverse events (AEs) from the time of Akynzeo® administration over a period of 5 days during the chemotherapy cycles which are part of the observation period will be documented on the appropriate pages of the eCRF.

A serious adverse event (SAE) is defined as an AE that:

- results in death;
- is life-threatening;
- requires hospitalization or prolongation of existing hospitalization;
- results in persistent or significant disability or incapacity;

---

 This includes every AE that – in the opinion of the investigator – is life-threatening for the study subject. This definition does not include events that may have led to death, if they had occurred in a more severe form.

- is a congenital anomaly or results in a birth defect or
- significant medical events that may endanger patients or require an intervention to prevent the above characteristics or consequences.

An unexpected adverse event is any event for which, with regard to its nature, severity or incidence, no details have been included to date in the current Product Monograph for Akynzeo®. The assessment of the "expectedness" of an AE is performed by the sponsor.

Planned surgical interventions or hospitalizations scheduled before the informed consent form was signed but carried out during the study period (study procedures, chemotherapy cycles, etc.) are not to be regarded as (serious) AEs.

The investigator assesses whether or not an event qualifies as a serious adverse event (SAE, see criteria above).

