			
 
 										
 
 dd	mmm	yyyy	hh	mm	hh	mm	
 
											dd	mmm	yyyy	hh	mm	hh	mm	
 
 				
 
 hh	mm	hh	mm	
 
					hh	mm	hh	mm
dd	mmm	yyyy	hh	mm	hh	mm																							
hh	mm	hh	mm																										

2. Were you hospitalized overnight during the 120 hours (5 days) after the start of chemotherapy?  
 No    Yes → If you were hospitalized overnight, please check the applicable box(es) or provide the reason, and record the date, onset time and end time of each overnight hospitalization.

Nausea	Vomiting	Other Reason	Date	Onset Time 00:00 – 23:59	End Time 00:00 – 23:59																								

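### The synopsis keeps nausea and vomiting out of the safety records with no exception for serious events and no explicit time limit, contradicting the CR definition and the safety sections

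*Combined protocol and SAP*

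**What the plan says.** The exclusion is in the synopsis, under secondary outcomes: "Safety parameters (failure of CR, i.e., nausea and vomiting will not be included in the safety records". The same list defines CR as "Complete Response (CR: no emetic episodes and no use of rescue medication) - overall – 0-120 hours (Day 1 to Day 5". Section 2.2 agrees ("Complete Response (CR): no emetic episode and no use of rescue medication in the overall period (0-120h/Day 1-5"), and so does Section 6.7 ("no emetic episode and no use of rescue medication during the observational period (Day 1 to Day 5").

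The body repeats an exclusion of nausea and vomiting in two places, Sections 3.1 and 6.8.2. Both concern the AE item of the Day 1-5 diary, which records nausea and vomiting separately.

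The safety sections carry no such exclusion:

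- Section 3.7 evaluates safety by the incidence and type of AEs, SAEs and AEs leading to discontinuation.
- Section 3.1 states: "Safety events occurring between chemotherapy cycles will be reported by the patient".
- Section 6.9 runs AE reporting from consent to 28 days after Visit 5. The opening of Section 8 states: "Adverse events will be collected from the time a subject has signed an ICF and followed until the end of study-visit 6".
- Section 8.1 makes an AE serious if it "requires hospitalization or prolongation of existing hospitalization". Section 8.3 requires every SAE, related or not, to be sent within 24 hours.

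Section 8.1 also says that AEs over 5 days from Akynzeo administration in each observed cycle go on the eCRF pages. That is shorter than the periods in Section 6.9 and the opening of Section 8.

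**The concern.** The purpose of the parenthesis is reasonable: an efficacy failure already captured in the diary should not be counted again as an AE. The wording goes further than that. It equates failure of CR with nausea and vomiting in general, which the protocol's own CR definition does not support, and it makes no exception for an event that meets an SAE criterion.

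Safety is a listed secondary outcome, reported as AE and SAE incidence. If one part of the protocol tells a site to leave an event out and another tells it to enter and report it, the incidence depends on which part the site followed. Up to 20 sites may take part. An event left out under the synopsis can only lower the AE and SAE counts for the product.

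**Working it through.** The protocol states no figure for this point, so there is nothing to reproduce. The check compares the definitions, applies them to four example records, and sizes the time window at issue.

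**1. Failure of CR and nausea or vomiting are different sets.** CR fails on emesis or rescue use within 0-120 h. Nausea without rescue is not a failure, and neither is vomiting after 120 h. Rescue use without vomiting is a failure. The Phase III figures in Section 1.4 (Study 2, NEPA arm, overall period) illustrate the last point: 100 - 74.3 = 25.7% failed CR and 100 - 79.8 = 20.2% vomited, so 25.7 - 20.2 = 5.5% failed CR without vomiting.

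**2. Four example records.**

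- *Nausea only on Day 2, no rescue.* Not a CR failure, although the synopsis treats it as one. The diary VAS records it, so it is not lost.
- *Non-serious vomiting on Day 3.* A CR failure, recorded in the diary and vomiting log, and left out of the safety records. This is the intended case.
- *Overnight admission for vomiting on Day 4.* A CR failure within 0-120 h, so the synopsis bars it from the safety records even on the time-limited reading. It is also an SAE under Section 8.1, reportable under Section 8.3 and counted under Section 3.7. These instructions cannot all be followed. The diary does ask "Were you hospitalized overnight during the 120 hours (5 days) after the start of chemotherapy", with vomiting as a listed reason, but that feeds the exploratory hospitalization table and not SAE incidence.
- *Non-serious vomiting on Days 8-9.* Not a CR failure. The diary, the vomiting log and the emergency department and hospital questions stop at 120 h, and FLIE asks about the past five days. AE reporting is the only route left. Sections 3.1, 6.9 and the opening of Section 8 admit the event; the literal synopsis wording and the 5-day window in Section 8.1 would each leave it out.

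**3. Share of time that depends on AE reporting.** The protocol gives no chemotherapy cycle length, so L is an assumption. The share of a cycle after Day 5 is (L - 5)/L:

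- L = 14: 9/14 = 64%
- L = 21: 16/21 = 76%
- L = 28: 23/28 = 82%

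Counting instead from Visit 2 to the full 28 days after Visit 5, the period is 3L + 28 days, of which the diary covers 4 x 5 = 20:

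- L = 14: (70 - 20)/70 = 50/70 = 71%
- L = 21: (91 - 20)/91 = 71/91 = 78%
- L = 28: (112 - 20)/112 = 92/112 = 82%

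Table 1 and Section 6.6 allow the final visit before the next cycle, so the true share may lie nearer the first set. On either count, most follow-up time lies outside the diary.

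**4. Number of events.** The protocol gives no rate of late or serious nausea or vomiting under this treatment, so no count of affected patients or SAEs follows from it.

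**The case against.** The strongest reply is that a bounded reading is available. The parenthesis speaks of failure of CR, which the same synopsis list defines over 0-120 h. Where the body repeats the exclusion, it attaches only to the Day 1-5 diary. Sections 3.1, 6.9 and 8 collect AEs between cycles and up to Visit 6, and Table 1 schedules an AE assessment at Visits 2 to 6, none with an exception for nausea or vomiting. The SAE rules have no exception either. Lack of efficacy is a special situation that Section 8.1 sends to the AE pages and Section 10 makes reportable within 24 hours. Stays within 120 h also reach the hospitalization tables, which use the Safety population.

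Much of this stands. A reader might infer that the study drops all nausea and vomiting from its safety result, that serious vomiting cannot appear there, and that late events appear in no result. The protocol does not support that: it is the outcome of one literal reading, and other sections point the other way.

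The reply does not remove the contradiction. The bounded reading still bars the Day 4 admission, which Sections 3.7, 8.1 and 8.3 require to be reported and counted. The lack-of-efficacy route adds another instruction at odds with the synopsis. For late events, the bounded reading leaves the 5-day window in Section 8.1 untouched. Section 7.3 defers analysis details to a statistical analysis plan and table mock-ups that are not part of the text reviewed, but neither could restore events that sites never entered.

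**Conclusion.** The concern holds as a contradiction between sections. The synopsis exclusion does not match the CR definition and conflicts with Sections 3.7, 6.9, 8.1 and 8.3. For serious nausea or vomiting on Days 1-5 the conflict exists on any reading. For events after 120 h it depends on whether a site follows the literal synopsis or the 5-day window in Section 8.1, as against Section 6.9 and the opening of Section 8. Such events can be lost or handled differently by site, and any loss would lower the AE and SAE counts.

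The window exposed is 64% to 82% of each cycle, resting on assumed cycle lengths of 14 to 28 days. That is a share of time, not of events, and it does not show that any given event will be lost. The plan should be corrected, because the affected result is a listed secondary outcome and the remedy is cheap.

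**What to change.** Replace the parenthesis in the synopsis with a bounded rule and repeat it in Sections 3.7 and 8.1. Suggested wording:

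*Non-serious nausea, retching and vomiting with onset 0-120 h after the start of chemotherapy in cycles 1-4 are diary efficacy data and are not also entered as AEs. Nausea, retching or vomiting with later onset, or meeting any SAE criterion at any time, is recorded and analysed as an AE or SAE.*

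State whether the exclusion governs collection or only tabulation. Have sites ask about late events at the AE assessments already scheduled for Visits 3 to 6.

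Reconcile the 5-day AE documentation window in Section 8.1 with Section 6.9 and the opening of Section 8. Without this, the new wording would require late vomiting to be recorded while the adjacent sentence leaves it outside the window.

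The cost is a wording amendment and an instruction in the eCRF completion guide, with no new visit or procedure. The downside is a few more AE entries and a slightly less favourable AE and SAE count.

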## 1 INTRODUCTION

This document is a protocol for a human research study.

This study will be carried out in compliance with the protocol, international standards of Good Clinical Practice (GCP) (ICH E6), Tri-council Policy Statement on Ethical Conduct for Research Involving Humans (CIHR 2010), applicable regulatory requirements and applicable Institutional research policies and procedures.

### 1.1 Background Information

Cancer chemotherapy is often associated with nausea and vomiting, which are among the most unpleasant and distressing side effects for subjects [1, 2]. Chemotherapy-induced nausea and vomiting (CINV) reduces patient's health-related quality of life (QoL) [3] and may cause noncompliance or refusal of potentially life-saving chemotherapeutic regimens [4]. The severity and pattern of nausea and vomiting induced by a chemotherapeutic regimen depend on the agents used and the doses employed [4]. Accordingly, chemotherapeutic regimens are classified as highly or moderately emetogenic [4].

CINV is classified as either acute (occurring within the first 24h after chemotherapy) or delayed (occurring after the first 24h, extending until 120h). Nausea and vomiting result from stimulation of a multi-step reflex pathway controlled by the brain. The vomiting reflex involves both central and peripheral components and the emetic response is integrated into the vomiting center [5].

The standard of care for antiemetic prophylaxis now consists of combinations of agents that inhibit several molecular pathways involved in emesis. The concomitant use of these agents is currently recommended for patients receiving chemotherapy of high emetic risk [6]. This regimen consists of a 5-hydroxytryptamine-3 (5-HT3) receptor antagonist (RA), a neurokinin-1 (NK1) RA and a corticosteroid, such as dexamethasone. Moreover, the Multinational Association of Supportive Care in Cancer and European Society of Medical Oncology MASCC/ESMO evidence-based guidelines recommend the triplet antiemetic regimen for carboplatin-based regimens [6]. The American Society of Clinical Oncology (ASCO) has also recently recommended the addition of olanzapine to this triplet regimen [7] in HEC.

